3.4 Study Duration and Schedule

Patients will partake in 7 visits over a 3 month period at the dermatological department of Bispebjerg Hospital (time schedule in Section 5):

- 1 Screening visit
- 1 Treatment day
- 5 Control visits after treatment on Day 1, 5, 14, 30 and Month 3

The study is expected to run between March 2018 - March 2019

Recruitment start	1. March 2018
Treatment start	1. March 2018
Final patient treatment	1. December 2018
Final control visit	1. March 2019

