4.1 Inclusion criteria

Subjects who meet all of the following criteria are eligible to participate in this study:

1. Histologically-verified, previously untreated superficial or nodular BCCs on the scalp, face, extremities or trunk
2. >18 years of age at baseline
3. Legally competent, able to give verbal and written informed consent
4. Subject in good general health, is willing to participate and can comply with protocol requirements.
5. Fitzpatrick skin phototype I-III
6. Female subjects of childbearing potential¹ must be confirmed not pregnant by a negative urine pregnancy test prior to trial treatment.

¹Female subjects are considered of childbearing potential unless they have been hysterectomized or have undergone tubal ligation or have been post-menopausal for at least one year prior to first visit.

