4.2 Exclusion criteria

Subjects meeting any of the following criteria are not eligible to participate in this study:

1. High-risk BCC
 - i. Tumors in the following anatomical locations: midface, orbital, ears
 - ii. Size: >20 mm in facial/scalp areas or > 50 mm in non-facial/non-scalp areas
 - iii. Subtype: morpheaform and micronodular BCC
 - iv. History: Gorlin syndrome or immunosuppression
2. Previous treatment of the BCC lesion
3. Known allergy to cisplatin or Efudix®
4. Other skin diseases present in the treatment area
5. Tattoo in the treatment area which may interfere with or confound evaluation of the study
6. History of keloids which is deemed clinically relevant in the opinion of the investigator
7. Fitzpatrick skin phototype IV-VI
8. Lactating or pregnant women

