4.4 Withdrawal Criteria

Subjects may withdraw from the trial for any of the following reasons:

1. Unacceptable treatment efficacy: the investigator is free to withdraw the subject at any time based on a medical judgment.
2. Unacceptable adverse events: any adverse event that the investigator or the subject considers unacceptable.
3. Exclusion criteria: any exclusion criteria which emerge/become apparent during the subject's participation in the clinical trial.
4. Voluntary withdrawal: subjects are free to withdraw from the clinical trial at any time and for any reason. If applicable, the subject's legal representative can withdraw the subject from the trial.

Subjects who discontinue treatment for any reason will be offered conventional BCC treatment and subsequent control according to national guidelines. Those who withdraw will be substituted. The research team will use already collected data after withdrawal unless the participant objects.

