5.2.4 Topical 5-Fluorouracil (5-FU)

After cisplatin removal, the well bandage is disposed of and a thick amount of Efudix® 5% 5-FU cream (Meda Pharmaceuticals A/S, UK) is applied to the entire test area (corresponding to up to 0.125 ml per cm² skin). After 5-FU application, transparent dermatological film (TegaDerm® film dressing, 3M Medical, MN, USA) is applied to the test area as an occlusive dressing. The cream is left on the skin until next control visit. Thus, on Day 1 and 5, Efudix cream is reapplied at the same dose. The cream is removed on Day 7 after AFL treatment.

STUDY SET UP	Visit 1 Screening	Visit 2 Treatment Day 0	Visit 3 Day 1	Visit 4 Day 5 +/- 2 days	Visit 5 Day 14 +/- 3 days	Visit 6 Treatment* Day 30 +/- 5 days	Visit 7 Month 3 +/- 5 days
Screening & enrolment							
Informed consent	✓						
Inclusion/exclusion criteria	✓						
Relevant medical history	✓						
Location of BCC	✓						
Pregnancy test when relevant		✓				✓	
Interventions							
AFL		✓				(✓)	
Apply topical cisplatin(60min)		✓				(✓)	
Apply 5-FU under occlusion		✓	✓	✓		(✓)	
Clinical LSR evaluation							
FDA-approved LSR scale		✓	✓	✓	✓	✓	
Clinical photos		✓	✓	✓	✓	✓	
Safety							
Clinical evaluation		✓	✓	✓	✓	✓	
Tumor size and clearance evaluation							
Clinical/dermoscopic photos		✓	✓	✓	✓	✓	
D-OCT		✓				(✓)	
RCM		✓					
HIFU		✓				(✓)	
Biopsy							✓

*Offered if BCC residual or recurrence; (✓): Treatment/technique can be relevantly applied if tumor residuals are identified clinically or by D-OCT/RCM and there is no crusting etc. LSR: Local skin reactions, RCM: Reflectance confocal microscopy, D-OCT: Dynamic optical coherence tomography

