8.1 Definitions

- Incident: any unwanted incident after treatment with a medical product occurring during the trial. Treatment and incident need not be related.
- Adverse Event (AE): Any unexpected medical event without known causal relation to the treatment will be reported as an AE. The event can be of any nature, an incident, a symptom or disease that is temporarily linked to the treatment of cisplatin/5-FU/AFL or the combination, whether or not it is considered related to exposure or not.
- Adverse Reaction (AR): A harmful or unforeseen reaction with a known or expected association to cisplatin/5-FU/AFL or the combination will be reported as an AR.
- Serious Adverse Event (SAE): An adverse event that results in death or leads to serious deterioration in the health of a subject, resulting in:
 - A life-threatening illness or injury, OR
 - A permanent impairment of a body structure or a body function, OR
 - Inpatient or prolonged hospitalization, OR
 - Medical or surgical intervention to prevent life-threatening illness or injury or permanent impairment to a body structure or a body function
 - an adverse event that leads to fetal distress, fetal death or a congenital anomaly or birth defect
- Unexpected Serious Adverse Effect (SUSAR): A serious adverse event that is unexpected according to the product summary, but suspected to be treatment-related (cisplatin/5-FU/AFL or the combination), will be reported as an SUSAR.

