8.2 Documenting and Reporting Adverse Events (AE) and Adverse Reactions (AR)

The investigators are responsible for routine assessments of AEs and ARs. All clinical complaints, symptoms, or signs that meet AE or AR definitions will be documented in the study record and the patient's medical record. Erythema and/or edema are anticipated sequelae of treatment; LSRs included in the LSR Grading Scale are reported as LSRs and not as AEs in the CRF, even if they require treatment. All AEs and ARs are described according to duration (start and end date), severity, association with drugs, whether further treatment is required and whether the AE has led to a serious adverse event. The location of the event is recorded as either "treated area" or "non-treated area". AEs and ARs will be followed until they have resolved.

The severity of an AE/AR is graded as:

- Mild: AE is transient and does not affect daily activities
- Moderate: AE causes patient discomfort and affect daily activities
- Severe: AE affect the patient's daily activities to a significant degree and may mean invalidity/incapacity for work or else be life-threatening.

The outcome of an AE/AR is described as:

- Resolved
- Improvement without sequelae
- Improvement with sequelae
- Persistent, follow-up necessary
- Persistent, follow-up not necessary

The investigators assessment of whether an AE is associated with the trial medication is classified as follows:

- Yes: an AE which after careful evaluation has a temporal association with the treatment and is in all probability related to the trial medication.
- No: an AE which after careful evaluation is definitely judged to be attributable to an external cause (disease, environmental exposure etc.) treatment and is in all probability related to the trial medication.

8.3 Documenting and Reporting of Serious Adverse Events (SAE) and Unexpected Serious Adverse Reactions (SUSAR)

The investigator is responsible for reporting all SAEs after the patient has signed the consent form until the final control visit. SAEs are reported within 24 hours to sponsor-investigator [name]

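### SAE reporting closes months before most outcomes of a pregnancy exposed in the trial can be known, although fetal death and birth defects are defined as SAEs

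*Combined protocol and SAP*

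**What the plan says.** **What is serious.** Section 8.1 includes among SAEs "an adverse event that leads to fetal distress, fetal death or a congenital anomaly or birth defect".

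**When it is reported.** Section 8.3 sets the period: "The investigator is responsible for reporting all SAEs after the patient has signed the consent form until the final control visit". It goes on to require that an SAE, once it has occurred, be followed until it resolves or stabilises, with no Month 3 limit. Section 8.2 has adverse events (AEs) and adverse reactions followed until resolution.

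**Which visit is last.** Section 3.4 (Study Duration and Schedule) gives each patient "5 Control visits after treatment on Day 1, 5, 14, 30 and Month 3". The visit table in section 5 puts a window of plus or minus 5 days on Month 3. The date table in section 3.4 also uses "Final control visit" for a single trial date, 1 March 2019.

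**Pregnancy.** Women of childbearing potential "must be confirmed not pregnant by a negative urine pregnancy test prior to trial treatment" (section 4.1). The visit-table row "Pregnancy test when relevant" is ticked at Day 0 and Day 30. Section 4.2 excludes "Lactating or pregnant women". Section 4.4 lists, among the reasons for which a subject may leave the trial, "any exclusion criteria which emerge/become apparent during the subject's participation in the clinical trial". For those who leave, it describes standard care of the tumour, replacement of the patient and use of the data collected so far. It does not say whether safety reporting continues.

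**The concern.** The definition and the reporting window do not fit each other. Section 8.1 names outcomes that are mostly seen late in pregnancy or at delivery, and section 8.3 ends the duty to report after about three months. Nothing in the text names a pregnancy as reportable or arranges for it to be followed to its outcome. An uneventful pregnancy still under way at Month 3 therefore triggers nothing further.

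At stake is how an absence of late fetal events in the final safety report (section 8.4) could be read: it might mean only that births were not followed. Section 11 says that this treatment has not been tested in patients before. Section 7.2 expects negligible systemic exposure, but on the basis of a pig study. The check in patients is one blood sample at 24 hours in 4 to 6 people (section 3.5).

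**Working it through.** The plan gives no figure on this point, so the check is date arithmetic.

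**Inputs from the protocol:** last patient visit Month 3, plus or minus 5 days; possible repeat treatment on Day 30; 5-FU left on for 7 days; treatment from 1 March to 1 December 2018; trial-level final visit 1 March 2019; safety report within 90 days of the end.

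**Assumptions not in the protocol:** Month 3 is Day 90, so the visit falls on Day 85 to 95; conception is at 2 weeks' gestation; a pregnancy missed by the Day 0 test is at 2 to 5 weeks then; term is 40 weeks (37 as the early limit).

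**1. Final visit read per patient.** Gestation at the last visit = gestation at Day 0 + visit day / 7.

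- Conceived on Day 0: 2 + 85/7 = 14.1 weeks to 2 + 95/7 = 15.6 weeks. Time left to 40 weeks: 25.9 to 24.4 weeks.
- Missed at Day 0, at 5 weeks then: 5 + 85/7 = 17.1 weeks to 5 + 95/7 = 18.6 weeks. Time left to 40 weeks: 22.9 to 21.4 weeks.
- Conceived on Day 30 to 37 (the repeat cycle, 30 + 7 = 37): from 2 + (85 − 37)/7 = 8.9 weeks to 2 + (95 − 30)/7 = 11.3 weeks. Time left to 40 weeks: 31.1 to 28.7 weeks.

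The smallest gap to a 40-week birth is 21.4 weeks. Even for a birth at 37 weeks it is 37 − 18.6 = 18.4 weeks.

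**2. Final visit read as 1 March 2019.** For a pregnancy at 2 to 5 weeks on Day 0, birth comes (40 − 2) × 7 = 266 to (40 − 5) × 7 = 245 days after Day 0.

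- Latest Day 0 with a birth by 1 March 2019: 8 June (266 days) to 29 June 2018 (245 days).
- Treatment runs for 275 days. Those dates are days 99 and 120 of it, so (275 − 99)/275 = 64% to (275 − 120)/275 = 56% of the treatment calendar is not covered.
- Later conception moves the limit earlier. With conception on Day 37, birth comes 37 + 266 = 303 days after Day 0, and the limit is 2 May 2018.
- For a patient treated on 1 December 2018, birth falls between 3 and 24 August 2019. The safety report is due by about 30 May 2019 (1 March + 90 days).

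**3. What falls inside the window.** On the per-patient reading, a fetal death or a prenatally detected anomaly before the Month 3 visit is a reportable SAE and is then followed to resolution. Later fetal death, distress during labour and defects first found at delivery are outside.

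**The case against.** **SAEs are followed until resolved.** This is true and has no time limit, but it applies to an event that has already met the definition. A pregnancy without complications at Month 3 has not. An investigator might log it as an AE and follow it, but nothing in section 8 asks for that.

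**The final control visit may be the trial-level date.** Section 3.4 allows this reading. It helps only patients treated early, as step 2 shows, and the double use of the term is itself a reason to define it.

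**Few women are concerned and the primary outcome is untouched.** The second part stands. The first is likely, but the documents give no number.

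A reader might also infer more than the documents support:

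- *That the category can never capture anything, so zero fetal events is guaranteed.* Early losses and early prenatal findings are captured.
- *That a woman who becomes pregnant must be withdrawn and her SAE reporting then stops.* Section 4.4 is permissive, and no text says that reporting ends at withdrawal.
- *That sections 8.1, 8.3 and 4.4 contradict each other.* All three can be applied together. The fault is one of fit and omission.
- *That no precautions apply between tests.* Consent material was removed from the text under review and may contain them.
- *That no test follows a repeat cycle.* The extracted table shows none, but its Month 3 column is visibly incomplete: it lists only the biopsy, although section 6 also schedules imaging then.

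**Conclusion.** The concern holds in a limited form: the stated SAE window closes before most outcomes of an exposed pregnancy can be known, and no reporting or follow-up of pregnancies to outcome is described, including after withdrawal. On the per-patient reading, a pregnancy present at Day 0 or conceived that day has about 21 to 26 weeks left to a 40-week birth when reporting ends, and one conceived later has longer. On the trial-level reading, births are covered only for patients treated by about June 2018 at the latest. The sizes depend on the assumed gestation at Day 0, the assumed term and Month 3 taken as Day 90, but no value in the ranges shown brings a term birth inside the per-patient window. The practical size cannot be computed, because the number of women of childbearing potential among the up to 24 patients is not given. This is a gap in safety capture that is worth closing; it does not affect the planned analyses.

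**What to change.** Reconcile sections 8.1, 8.3 and 4.4:

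- In 8.3, make any pregnancy found between Day 0 and the final visit reportable to the sponsor.
- In 8.3, keep the reporting period open for fetal and birth outcomes until the outcome is known.
- In 4.4, state that this continues after withdrawal, with the participant's agreement.
- State whether the final control visit in 8.3 is the patient's own Month 3 visit or the trial-level date.

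The cost is protocol wording and some extra follow-up for what is probably a very small number of women. An outcome that arrives after the 90-day safety report would need a supplement to it. Any further pregnancy testing, and any requirements between tests, are for the sponsor to decide; none is proposed here.

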8.4 End of Trial Reporting

At the end of the trial, a final report with all AEs, ARs, SAEs, and SUSARs is handed to the Danish Health and Medicine Authority and the Regional Committee on Health Research Ethics, latest 90 days after conduction. If the trial ends ahead of schedule, a report will be submitted to the above-mentioned instances within 15 days. The results from the trial will also be sent to the Danish Health and Medicine Authority and the Regional Committee on Health Research Ethics latest one year after completion.

9. Statistics

9.1 Sample size

The primary objective of this explorative trial is to investigate tolerability of AFL-assisted cisplatin+5-FU to ensure that intolerable/severe or serious related adverse events remain minimal for the observed efficacy. While no formal statistical calculation has been performed, 12 superficial and 12 nodular BCCs in 24 subjects are considered sufficient to estimate benefit/risk of the treatment.

9.2 Study populations

Treated study participants are divided into the following populations:

Per-protocol (PP) population:

Includes only patients that have completed all control visits as planned. Larger deviations such as

breach of inclusion criteria, inadequate outcome assessment or larger differences in treatment, are assessed before statistical analysis is conducted.

Intention-to-treat (ITT) population:

Includes all patients that have received treatment. In the event of missing data, the population is analyzed using the “last observation carried forward” approach to minimize bias associated with loss to follow up.

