3.4 Summary of Outcome Measures and Methods

Outcome measures and methods/techniques are summarized below. Detailed descriptions are presented in Section 6 and Table 1 (Appendix 1).

Primary outcome:

To investigate tolerability of topical AFL-assisted cisplatin+5-FU therapy for BCC by evaluating:

- I. Severity and duration of clinical local skin reactions including erythema, edema, scabbing, flaking and pustulation assessed by a physician using an established 0-4 point scale (none, mild, moderate, severe) from 0-30 days post-treatment.

- II. Occurrence of side effects (prolonged erythema/edema, hyper/hypopigmentation, scarring and infection) up to 3 months post-treatment.

Secondary outcome:

- 1) To monitor BCC tumor size and clearance based on clinical assessments and dermoscopy, supported by non-invasive imaging techniques including dynamic optical coherence tomography (D-OCT), reflectance confocal microscopy (RCM), high intensity focused ultrasound (HIFU) and histological analysis up to 3 months post-treatment.

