6.3 Methods for Outcome Assessment

6.3.1 Clinical Evaluation and Digital Photography

Clinical evaluation of LSRs (erythema, edema, flaking, crusting/scabbing and pustulation) in treated areas will be performed by a non-blinded physician using a FDA-approved LSR scale at Days 1, 5, 14 and 30 after baseline. The scale assesses severity of individual LSR parameters on a 0-4 points scale: none, mild, moderate, severe. Tumor size (mm) and clearance (yes or no) will also be evaluated by standard clinical dermoscopy at Day 30 and Month 3 (Appendix 1). Digital photography using a Canon Camera will be performed prior to, during, after treatment, and at control visits under standardized conditions. All images are assigned an ID-number and anonymized.

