7.2 Topical Cisplatin and 5-FU

Storage, handling, personal protective equipment and disposal of chemotherapeutics as outlined by hospital guidelines, will be followed. Neither cisplatin nor 5-FU will come in contact with mucus membranes.

The side effect profile associated with intravenous cisplatin+5-FU therapy is not anticipated, as neither cisplatin nor 5-FU has been detected in the blood of live pigs measured hourly from 0-5 hours, 48 and 120 hours after topical AFL-assisted cisplatin+5-FU exposure. In that study, treatment consisted of a similar schedule/dose applied over a significantly larger skin area (>100 cm²). In this study, negligible systemic drug exposure is thus expected, an element that will be reassessed in the described preliminary study. On the other hand, transient local effects are common and expected after AFL-assisted cisplatin+5-FU on skin, likely to resolve within 30 days. When administered alone, AFL+cisplatin caused redness and edema peaking 48 hours after topical exposure, followed by a healing response. Using the combination of AFL-cisplatin+5-FU, the anticipated pattern is an early inflammatory phase characterized by erythema, a necrotic phase characterized by skin erosion, and finally healing (re-epithelialization). Local treatment effects can

be notable with blistering/ulceration. Estimated incidences after topical treatment with the two drugs are:

- Mild to moderate erythema (94-100%)
- Mild to moderate edema (33-99%)
- Scabbing (50-95%)
- Erosion (50-95%)
- Hypo/hyperpigmentation resolved after 1-3 months (30%)
- Pruritus (20%)
- Erythema lasting greater than 12 weeks (5%)
- Exudate, bleeding or crusting (1%)
- Infection (1%).
- Allergy (1%)
- Temporary hair loss in the treated area (<1%)

Dihydropyrimidine dehydrogenase (DPD) deficiency is an extremely rare genetic condition that renders 5-FU toxic to affected individuals. Toxicity typically presents within 96 hrs of administration. While extremely unlikely to occur due to the uncommonness of the mutation and the minimal levels of 5-FU anticipated to permeate into the systemic circulation, investigators will stay vigilant about this potential risk.

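### Carrying the last value forward for all missing ITT data does not suit healing skin reactions or Month 3 clearance

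*Combined protocol and SAP*

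**What the plan says.** Section 9.2 defines the ITT set as all treated patients and handles missing data there with one rule, the "last observation carried forward" "approach to minimize bias associated with loss to follow up". It makes no distinction by endpoint, visit or reason for loss. The PP set "Includes only patients that have completed all control visits as planned". Neither set is named as primary, and no other missing-data method or sensitivity analysis is described.

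The first part of the primary outcome (section 3.4, Summary of Outcome Measures and Methods) is "Severity and duration of clinical local skin reactions" up to Day 30, scored on the "FDA-approved LSR scale at Days 1, 5, 14 and 30 after baseline" (section 6.3.1). Section 7.2 calls "transient local effects are common and expected after AFL-assisted cisplatin+5-FU on skin, likely to resolve within 30 days", and describes inflammation, then a necrotic phase, then healing. On 5-FU, section 5.2.4 says: "The cream is removed on Day 7 after AFL treatment".

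Tumour clearance, a secondary outcome, is assessed clinically and by imaging at Day 30 and Month 3 (section 6.2). Histology is planned at Month 3 only (sections 6.2 and 6.3.3). A repeat treatment is offered at Day 30 if tumour persists (section 3.3). Patients may leave because of an unacceptable adverse event, and those who withdraw are replaced (section 4.4).

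**The concern.** LOCF is neutral only if a patient's status stays the same after the last visit. The protocol expects the opposite for skin reactions. The Day 1 visit, and the Day 5 visit with its window of plus or minus 2 days, both fall no later than Day 7, so their scores describe skin under 5-FU. Carried to Day 14 or Day 30, such a score can turn a healed reaction into an unhealed one and lengthen its duration. A Day 1 score carried to Day 5 can err in either direction. Loss may also be related to the reaction itself, given the withdrawal criteria.

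For clearance, sections 8 and 11 treat Month 3 as the point at which tumour removal is confirmed. LOCF lets an unconfirmed Day 30 finding of clear count there, and it carries a Day 30 finding of not clear past any repeat treatment. It has no clear meaning for histology. Section 9.1 sets out to estimate benefit against risk, and the rule can distort both sides of that balance in groups of about 12.

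**Working it through.** **Inputs.** Section 9.1 plans 12 superficial and 12 nodular tumours, with no formal calculation. The plan contains no figure that depends on LOCF, so there is none to reproduce. The number lost in one subtype group, k = 1, 2 or 3, is an assumption.

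**1. Share unhealed at Day 30.** Suppose all patients have truly healed and k were last seen on Day 5 with a non-zero score. The true share unhealed is 0%.
- LOCF, 12 treated: k/12 = 8.3, 16.7, 25.0%.
- LOCF, lost patients replaced: k/(12+k) = 7.7, 14.3, 20.0%.
- The median Day 30 score stays at 0. With carried scores of 2 or 3, the mean runs from 2×1/12 = 0.17 to 3×3/12 = 0.75.

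**2. Duration.** Suppose every reaction truly resolves at the Day 14 visit and carried-forward patients count as 30 days, which is a lower bound for them. The mean is ((12−k)×14 + 30k)/12 = 15.3, 16.7, 18.0 days against a true 14.0. The median stays at 14.

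**3. Day 1 carried to Day 5, 12 treated.**
- Grades truly rise from 2 to 3: ((12−k)×3 + 2k)/12 = 2.92, 2.83, 2.75 against 3.0, an understatement.
- Grades truly fall from 3 to 2: ((12−k)×2 + 3k)/12 = 2.08, 2.17, 2.25 against 2.0, an overstatement.

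**4. Month 3 clearance under three rules.** Suppose 8 patients are observed clear at Month 3, and k are missing who were clear at Day 30, of 12 treated.

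| k | LOCF, (8+k)/12 | Missing as not cleared, 8/12 | Observed only, 8/(12−k) |
|---|---|---|---|
| 1 | 75.0% | 66.7% | 72.7% |
| 2 | 83.3% | 66.7% | 80.0% |
| 3 | 91.7% | 66.7% | 88.9% |

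The first two columns differ by k/12, or 8.3 points per patient. This compares two conventions; neither is the truth.

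**5. Expected error for one such patient of 12.** Let r be the probability that a patient clear at Day 30 is not clear at Month 3, assumed to be 10 to 30%.
- LOCF overstates by r/12 = 0.8 to 2.5 points.
- Missing as not cleared understates by (1−r)/12 = 7.5 to 5.8 points.
- The two errors are equal at r = 50%.

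**6. Histology.** No outcome biopsy precedes Month 3. LOCF therefore leaves the result missing, or falls back on the tumour-positive diagnosis required for entry by section 4.1. The plan does not say which.

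**The case against.** The trial is small, uncontrolled and exploratory, and gives no dropout rate, so every magnitude here is assumed. For tolerability, a longer apparent duration errs against the treatment. Section 9.3 allows medians and IQRs, and the median holds in the examples above. The PP set already gives a near-equivalent of the observed-case result at Month 3. All of this stands, and it limits the size of the point. It does not make LOCF suitable: the plan also allows means, and it reports severity and duration as primary without saying which analysis set leads.

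The strongest objection concerns clearance. Counting missing as not cleared lies further from the truth than LOCF unless more than half of Day 30 clears are lost by Month 3. That is correct. The convention is defensible only as a deliberately conservative one, shown beside the observed-case rate.

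A reader might also infer from the footnote to the study set-up table in section 5.2.4 that Day 30 D-OCT and HIFU are done only in patients with residual tumour, so that scans not done would be filled with the baseline tumour. The footnote reads "Treatment/technique can be relevantly applied if tumor residuals are identified clinically or by D-OCT/RCM and there is no crusting". It thus names imaging as a means of finding residual tumour, and section 3.3 bases the Day 30 decision on clinical evaluation and imaging together. The documents do not support that inference.

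**Conclusion.** The point holds in a limited form. As written, LOCF contradicts the protocol's own expected course for the primary skin-reaction outcome, and it may not reduce bias as section 9.2 intends. If 1 to 3 of 12 patients are lost after Day 5 and all have truly healed, 8.3 to 25.0% are recorded as unhealed at Day 30. LOCF does not change the worst observed grade.

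For clearance, a reader might take the 8.3 to 25.0 point spread between rules as the amount by which LOCF inflates the result. The documents do not support that. The spread supposes that every missing patient was clear at Day 30, and it measures rule against rule. On the assumed 10 to 30% range, expected overstatement is 0.8 to 2.5 points per missing patient of 12. The clearance point applies to clinical and dermoscopic assessment, and to imaging only where a Day 30 value exists. For histology the rule is undefined. The change should be made before the data are analysed, but the point does not threaten the trial's design.

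**What to change.** Replace LOCF in section 9.2 with a rule for each endpoint.

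- **Local skin reactions:** report observed scores by visit with the number assessed, plus worst observed grade. Report duration from onset to the first later visit with resolution, censored at the last skin-reaction visit attended. Show the number of losses and their reasons. As a sensitivity analysis, count patients who left because of a reaction as unresolved at Day 30.
- **Side effects to 3 months:** report any observed occurrence among all treated patients, with the number followed to Month 3.
- **Tumour size:** report as observed at each visit, with no carry-forward from baseline or across the Day 30 repeat treatment.
- **Month 3 clearance:** do not carry Day 30 values forward. Report all treated patients with missing counted as not cleared, labelled as conservative, beside the observed-case rate. Use the same rule for every method.
- **Analysis sets:** state the denominator including substituted patients. Name all treated patients as the primary set and PP as supportive.

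The cost is wording and minor analysis, with no new visits or patients. Against LOCF, reported clearance falls by one patient (8.3 points of 12) for each patient clear at Day 30 and missing at Month 3. Histological clearance also falls for any missing biopsy that LOCF would have left missing: with 8 clear and 2 missing of 12, from 8/10 = 80.0% to 8/12 = 66.7%.
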